Study Design	
This trial is a multi-center, randomized, double-blind, double-dummy, placebo-controlled study, consisting of 5 weeks of treatment. Eligible subjects for this study must have a diagnosis of probable Alzheimer's disease (AD) and must have clinically meaningful agitation secondary to AD. Following screening procedures for assessment of inclusion and exclusion criteria, eligible subjects will be randomized in a 1:1:1 ratio to be treated with AXS-05, bupropion sustained release (SR), or placebo. As part of protocol amendment 2, randomization to the bupropion arm was discontinued.
 
The primary efficacy endpoint is the change from baseline to Week 5 in the Cohen-Mansfield Agitation Inventory (CMAI) total score.
  
Screening Period
 
Prior to randomization, all potential subjects will enter an up to 4-week screening period (Screening) to determine eligibility. In order to be eligible, subjects must have a diagnosis of probable AD according to the 2011 National Institute on Aging-Alzheimer Association (NIA-AA) criteria, and a diagnosis of agitation according to the International Psychogeriatric Association (IPA) provisional definition of agitation.
 
Eligible subjects must have symptoms of agitation (intermittently or constantly) at the time of screening and for at least 2 weeks prior to randomization, and the agitation symptoms must be severe enough such that they interfere with daily routine and for which a prescription medication is deemed indicated, in the opinion of the current treating physician.
  
Treatment Period
 
Randomization
 
Eligible subjects who successfully complete Screening will be randomly assigned at the baseline visit (Baseline) to receive AXS-05, bupropion SR, or placebo, orally, twice daily, in a 1:1:1 ratio, for 5 consecutive weeks. As part of protocol amendment 2, randomization to the bupropion arm was discontinued.
 
The randomization schedule will be computer-generated using a permuted block algorithm that will randomly allocate the study drug to randomization numbers. The randomization will be stratified by region (US or Ex-US) and by antipsychotic use (yes or no).

Treatments

Doses will be titrated as follows:

- AXS-05 group: 105 mg bupropion/45 mg dextromethorphan BID
- Bupropion group: 105 mg bupropion BID
- Placebo group: placebo BID

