
Statistical Methods
	
Analysis Populations:
 
The following analysis populations are planned for this study:
 
 
▪ Modified Intent-to-Treat (mITT) Population—the mITT will be the primary efficacy analysis population and will consist of all subjects who are randomized, subsequently take at least 1 dose of the study drug, and have at least 1 post-Baseline efficacy assessment
 
▪ Intent-to-Treat Population—the ITT will include all subjects who are randomized
 
▪ Safety Population—the Safety Population will be the primary safety analysis population and will include all subjects who receive at least 1 dose of the study drug
 
 
Primary Efficacy Analysis:
 
The primary endpoint will be the change from Baseline (Day 1) to Week 5 in the CMAI total score. The primary comparison will be AXS-05 versus placebo.
 
The changes from Baseline in the CMAI total score will be analyzed using a Mixed Model with Repeated Measures (MMRM). This model will include treatment, week, and treatment-by-week interaction as factors, Baseline value as a covariate, and subject as a random effect. Treatment effects and the differences between treatments will be estimated using the least-square mean estimates and will be reported together with the 2-sided 95% confidence interval of the treatment difference. The null hypothesis of no treatment difference will be tested at a two-sided significance level of 0.05.
 
Safety Analysis:
 
Adverse events will be coded by system organ class (SOC) and preferred term using the Medical Dictionary for Regulatory Activities (MedDRA) reporting system. TEAEs are those that occur following the start of treatment with study drug through follow up (7 days after the last dose), and SAEs that occur from the start of treatment with study drug through 30 days after the last dose. The number and percentage of subjects with TEAEs will be displayed for each treatment group by SOC and preferred term. Additionally, TEAEs will be tabulated for each treatment group by severity and by relationship to the study drug. A listing of SAEs will be provided if applicable.
 
Descriptive summaries will be calculated, and data listings provided for hematologic, biochemical, and urinalysis laboratory parameters, and vital signs measurements, as appropriate.

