
Sample Size Determination
	
Approximately 300 completed subjects (100 per treatment group) will provide 90% to detect a treatment difference for the primary efficacy variable (change from baseline in CMAI total score at Week 5) at a two-sided significance level of 0.05. In the sample size calculation, it was assumed the effect size was 0.46. Approximately 435 subjects (145 subjects each in the AXS-05, bupropion SR, and placebo arms) will be randomized to achieve approximately 300 completed subjects, assuming an approximately 30% drop-out rate. As part of protocol amendment 2, randomization to the bupropion arm was discontinued.

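### Randomization is stratified by region and antipsychotic use, but the primary CMAI model in the synopsis includes neither factor; if they predict CMAI change, the reported standard error is somewhat too large.

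*Combined protocol and SAP*

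**What the plan says.** All references are to the synopsis of the combined protocol and SAP.

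- **Study Design, Randomization.** "The randomization schedule will be computer-generated using a permuted block algorithm", and "The randomization will be stratified by region (US or Ex-US) and by antipsychotic use (yes or no"). Two binary factors give four strata.
- **Statistical Methods, Primary Efficacy Analysis.** The endpoint is change from baseline to Week 5 in CMAI total score, analysed by MMRM. "The primary comparison will be AXS-05 versus placebo". The terms are listed in one sentence: "This model will include treatment, week, and treatment-by-week interaction as factors, Baseline value as a covariate, and subject as a random effect". The test is two-sided at 0.05.
- **Sample Size Determination.** "Approximately 300 completed subjects (100 per treatment group) will provide 90" per cent power, and "it was assumed the effect size was 0.46". The number randomized, 435 or 145 per arm, is set "to achieve approximately 300 completed subjects, assuming an approximately 30% drop-out rate".

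The model sentence shows no redaction. Nothing in the available text adds region or antipsychotic use to the model, plans a stratified sensitivity analysis, or explains why the factors are left out.

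**The concern.** The analysis does not follow the randomization. Stratified permuted blocks hold the two factors nearly equal between arms, so differences between strata contribute little to the true variability of the treatment difference. A model that omits the factors leaves those differences in the residual and computes its standard error as if they could have fallen unevenly.

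This matters only if the strata predict CMAI change beyond what baseline CMAI, already in the model, explains. That is plausible for antipsychotic use: inclusion criterion 14 names antipsychotics among the allowed treatments for agitation secondary to AD, so users entering the trial are still agitated despite treatment for the symptom being measured.

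At stake are the standard error, confidence interval and p-value of the primary result. Dropout also disturbs the stratum balance, which adds a small real loss of precision that fitting the factors would recover.

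**Working it through.** **Inputs from the synopsis.** 100 completers per group, effect size 0.46, two-sided alpha 0.05, about 30% dropout, 145 randomized per arm.

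**Input assumed.** R² is the share of residual Week 5 variance, after baseline CMAI, explained by the two factors. The documents give no value, so 2% to 10% is used. The effect size of 0.46 is kept on the SD without the strata.

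**Step 1: reproduce the plan's figure.** 0.46 × √50 = 3.253, and 3.253 − 1.96 = 1.293. Power = Φ(1.293) = 90.2% (89.9% from the noncentral t). The stated 90% with 100 per group reproduces. For dropout, 100 / 0.70 = 143 per arm against the stated 145.

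**Step 2: effect of the omission.** Let k be the fraction of the stratum variance that balance removes from the treatment difference: k = 1 for perfect balance, k = 0.7 after 30% random dropout.

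- SE overstatement = 1/√(1 − kR²) − 1
- Actual level = 2 × [1 − Φ(1.96/√(1 − kR²))]
- Power without strata = Φ(1.293/√(1 − kR²))
- Power with strata = Φ(3.253/√(1 − R²) − 1.96)

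| k | R² | SE overstated | Actual level | Power without | Power with | Difference (points) |
|---|---|---|---|---|---|---|
| 1 | 2% | 1.0% | 4.8% | 90.4% | 90.8% | 0.3 |
| 1 | 10% | 5.4% | 3.9% | 91.3% | 92.9% | 1.6 |
| 0.7 | 2% | 0.7% | 4.8% | 90.4% | 90.8% | 0.4 |
| 0.7 | 10% | 3.7% | 4.2% | 91.0% | 92.9% | 1.9 |

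Differences are taken before rounding. At R² = 0 the two models agree.

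**Step 3: simulation of the MMRM.** There were 10,000 replicates per scenario, with two arms of 145, blocks of 4 in four strata, visits at Weeks 1, 2, 3 and 5, 31% monotone random dropout (1 − 300/435 = 31%), unstructured covariance and a z reference. Assumed: 70% US, 25% antipsychotic users, R² split equally between the factors, residual correlation 0.6 between visits.

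| R² | Mean reported SE without / with strata | Power without / with |
|---|---|---|
| 0 | 0.131 / 0.131 | – |
| 2% | 0.131 / 0.130 (0.8% larger without) | 94.4% / 94.7% |
| 10% | 0.130 / 0.1245 (4.5% larger without) | 95.0% / 95.9% |

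At R² = 10%, the model without the strata reports an SE 1.035 times the empirical SD of the estimate and has a level of 4.6%. With the strata the simulated level was 5.5% (Monte Carlo SE about 0.2 points). The empirical SDs are nearly equal, 0.1257 against 0.1255, so most of the loss lies in the reported SE rather than in the estimate. Power exceeds the formula values because the MMRM uses partial data from dropouts.

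With stratum effects that grow over the weeks to R² = 10% at Week 5, power was 94.7% without the strata, 95.5% with two main effects and 95.8% with strata-by-week terms. The level was 4.2% without the strata and 4.9% with them.

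**Step 4: independent check.** A Week 5 ANCOVA was simulated under stratified blocks of 4, with 100 completers per arm, no dropout, and assumed prevalences of 80/20 for region and 20/80 for antipsychotic use. At R² = 10% the model without the strata reported a mean SE of 0.142 against an actual SD of 0.135, with a level of 3.8%. With the strata, the reported SE was 0.134 and the level 5.0%. At R² = 5% the levels were 4.3% and 4.9%.

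**The case against.** The strongest reply is that nothing here harms validity. The error is in the conservative direction, depends on a relation the documents do not quantify, and may be very small. Four points deserve weight.

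- **The upper end of the range is demanding.** With 70% US, 25% antipsychotic users and R² split equally, R² = 10% needs a region effect of √(0.05/(0.7 × 0.3)) = 0.49 residual SD and an antipsychotic effect of √(0.05/(0.25 × 0.75)) = 0.52 SD. Both exceed the 0.46 the trial is powered for. R² = 2% needs 0.22 and 0.23 SD. Ex-US means only Canada and Australia, and antipsychotic doses must be stable for at least 4 weeks. This stands: the low end of the range is the safer guide, and there the loss is negligible.
- **Part of the simulated power gain at R² = 10% reflects test size.** The comparison of 95.0% with 95.9% sets a test at 4.6% beside one at 5.5%. Moving the latter to 5% shifts its critical value from 1.919 to 1.96 and lowers its power to about Φ(1.739 − 0.041) = 95.5%, a gap near 0.5 points. This also stands. The 5.5% probably owes something to the z reference; the other simulations with the strata gave 4.9% to 5.0%.
- **The dropout formula overstates the real loss of precision.** It implies a true SD larger by √(0.93/0.90) − 1 = 1.7%, whereas the MMRM simulation shows 0.2%. For the planned MMRM, the simulated 0.3 to 0.9 points of power is the better guide than 0.4 to 1.9.
- **Only the synopsis and schedule were available.** A fuller statistical section may list the strata. If it does, the synopsis sentence still needs to agree with it.

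These points limit the size of the problem. None of them supplies a reason to leave out factors that the randomization used.

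**Conclusion.** The concern holds. The synopsis stratifies on two factors and specifies a primary model without them. If those factors predict CMAI change beyond baseline CMAI, the primary result is reported with mildly too little precision. For an assumed R² of 2% to 10%, the formulas put the overstatement of the SE at 0.7% to 5.4% across the two balance cases, and the power given up at 0.3 to 1.9 points. In the MMRM simulation the SE is 0.8% to 4.5% larger without the strata and power is 0.3 to 0.9 points lower. At R² = 0 there is no effect.

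The omission causes no inflation of type I error and no threat to the planned 90% power. It is an avoidable inefficiency, worth correcting because correction is nearly free. Confidence in the size is only moderate, since R², the stratum prevalences and random dropout are all assumptions.

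**What to change.** Add region (US / Ex-US) and antipsychotic use (yes / no), as coded at randomization, as fixed effects in the primary CMAI MMRM, and align the synopsis with any fuller statistical section. If the sponsor prefers to leave them out, the plan should say why. Two main effects are enough: in the simulation with stratum effects growing over time they recovered most of the gain available from strata-by-week terms.

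The change should be made before unblinding, because covariates added later would look data-driven. It costs one sentence and two model degrees of freedom. No new data are needed, since both factors define the randomization strata and are recorded for every randomized subject.

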**Schedule of Assessments**

Visit	Screening Visit 1	Baseline Visit 2	Visit 3	Visit 4	Visit 5	Visit 6 / ET a	Follow-up b Visit 7
Study Day	-28 to -1	1	8 (±3)	15 (±3)	22 (±3)	36 (±3)	43 (±3)
End of Week	Weeks -4 to -1		Week 1	Week 2	Week 3	Week 5	Week 6
Informed consent	X						
Inclusion/exclusion criteria	X	X					
Medical history and demographics	X						
Physical examination c	X					X	
Vital signs d	X	X e	X	X	X	X	
Electrocardiogram	X					X	
Review previous and concomitant medications	X	X	X	X	X	X	X
Height and weight	X					X	
Clinical laboratory tests f	X					X	
Columbia Suicide Severity Rating Scale (C-SSRS)	X	X	X	X	X	X	
Randomization		X					
Cohen-Mansfield Agitation Inventory (CMAI)		X	X	X	X	X	
Modified Alzheimer's Disease Cooperative Study-Clinical Global Impression of Change for Agitation (mADCS-CGIC)		X				X	
Administer first dose of study medication in clinic		X h					
Administer last dose of study medication in clinic						X	
Review of adverse events		X i	X	X	X	X	X
Blood sample for drug concentration				X		X j	
Blood sample for CYP2D6 genotyping		X					
Caregiver to Complete Daily Caregiver Diary g		X	X	X	X	X	
Review and return study medication and Caregiver Diary			X	X	X	X	
Dispense study medication		X	X	X			

- a Early Termination (ET) visit for subjects who withdraw prior to study completion, the Follow-up Visit will occur 1 week after ET.
- b Follow up visit may be conducted by phone. If the patient reports AEs that require follow-up an in-clinic visit should be performed.
- c A complete physical examination (excluding breast and genitourinary examination) will be performed at Screening and a brief physical examination will be performed at Week 5 or at Early Termination.
- d Vital signs, including seated and orthostatic blood pressure and pulse, respiratory rate, and oral temperature, will be measured.
- e On Day 1, vital signs should be collected pre-dose and at least 1 hour following the dose.
- f Clinical laboratory tests will include hematology, serum chemistry, and urinalysis.
- g A Caregiver Diary will be used to record the number of tablets of study medication and rescue medication (lorazepam) administered and the time of administration, adverse events, and subject behaviors. Study personnel will train caregivers how to complete the diary, retraining to occur as needed.
- h Subjects should be monitored in the clinic after the first dose. At a minimum, vital signs should be recorded 1 hour following the dose. If any changes in the subjects health status, subjects should stay in clinic for at least 3 hours following the dose and have additional safety assessments performed, such as ECG evaluation and/ or serum electrolytes, as appropriate.
- i During Week 1, sites are encouraged to contact subjects by phone to review and follow up on AEs.
- j At visit 6, a pre- and post-dose (within 3 hours after dosing) sample should be collected.

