## 1. SYNOPSIS

CLINICAL STUDY SYNOPSIS: AXS-05-AD-301	
Product Name/ Number	AXS-05 (bupropion hydrochloride and dextromethorphan hydrobromide monohydrate)
Protocol Number	AXS-05-AD-301
Protocol Title	A Randomized, Double-blind, Placebo-controlled Trial to Assess the Efficacy and Safety of AXS-05 for the Treatment of Agitation in Subjects with Dementia of the Alzheimer's Type
Indication	Treatment of agitation associated with dementia of the Alzheimer's type
Development Phase	2/3
Objective	The primary objective of the study is to evaluate the efficacy and safety of AXS-05 compared to placebo and bupropion sustained release (SR) for the treatment of agitation in subjects with dementia of the Alzheimer's type.

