All doses will be taken at least 8 hours apart, orally on an empty stomach (at least 2 hours pre- or post-prandial) with water.

All study medication including AXS-05 tablets, bupropion SR tablets, and placebo tablets are of identical appearance in order to maintain the integrity of the blind.

Rescue Medication

Patients will be allowed to receive oral lorazepam as rescue medication for the short-term treatment of symptoms of agitation if deemed necessary by the investigator. Lorazepam (0.5 mg tablets) will be administered in a total dose up to 1.5 mg/day and not to exceed 3 days in a 7-day period. Caregivers must record concomitant use of lorazepam in the Caregiver Diary.

Assessments and Visits

[figure not shown]
Study visits will occur at Screening (Visit 1), Baseline (Day 1, Visit 2), and on Days 8, 15, 22, 36 (Visits 3-6). Study procedures will be performed, and questionnaires for the evaluation of efficacy parameters will be administered during study visits. A safety follow-up phone call (Visit 7) will be conducted 1 week after the last dose of study drug (Day 43).

Caregivers will be provided with a Caregiver Diary at each study visit and will be instructed to record daily 1) any agitated or abnormal behaviors if they occur, including the number of times they occurred that day, 2) the number of tablets of study medication taken and the time of administration, 3) the dose of rescue medication administered and the time of administration if administered, and 4) any changes in the subject's physical status or mental status such as, dizziness, unusual weakness, falls, confusion or obvious worsening of memory problems, worsening agitation, any loss of consciousness, or seizures. Diaries will be reviewed during study visits.

A blood sample for cytochrome P450 2D6 (CYP2D6) genotyping will be collected at the Baseline visit. Blood samples for measurement of study drug concentrations will be collected on Day 15 (Visit 4) and on Day 36 (Visit 6).

The study design is summarized in the Figure below.

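### Does timing the follow-up visit from early termination, rather than from the last dose, leave the TEAE window undefined for subjects who withdraw?

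*Combined protocol and SAP*

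**What the plan says.** Three places bear on when safety follow-up ends.

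- **Schedule of Assessments, footnote a** (attached to the Visit 6 / ET column): "Early Termination (ET) visit for subjects who withdraw prior to study completion, the Follow-up Visit will occur 1 week after ET".
- **Synopsis, Assessments and Visits:** "A safety follow-up phone call (Visit 7) will be conducted 1 week after the last dose of study drug (Day 43").
- **Synopsis, Statistical Methods, Safety Analysis:** "TEAEs are those that occur following the start of treatment with study drug through follow up (7 days after the last dose"). Serious events have a separate window of 30 days, counted from the last dose.

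Two further items in the schedule bear on whether the last dose and the ET visit share a day. The row "Administer last dose of study medication in clinic" carries an X, without a footnote, in the column that Visit 6 and ET share. Footnote j says "At visit 6, a pre- and post-dose (within 3 hours after dosing) sample should be collected" and does not mention ET. Footnote c, by contrast, names early termination expressly for the closing physical examination.

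**The concern.** One visit seems to have two anchors. For a subject who stopped tablets some days before attending the ET visit, footnote a counts a week from that visit and the synopsis counts a week from the last tablet. The TEAE definition names both the follow-up contact and the seven-day limit, as if they were always the same date. A non-serious event starting after the seven days but before the follow-up contact would then be treatment-emergent on one reading and not on the other.

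Safety is part of the main aim: "The primary objective of the study is to evaluate the efficacy and safety of AXS-05 compared to placebo". The sample size text plans for many withdrawals, "assuming an approximately 30% drop-out rate". If the window ended at the visit, withdrawn subjects could be observed for longer after their last dose than completers, and unequal dropout would carry that difference into the comparison of arms.

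A lesser strand concerns the same column. The synopsis and schedule name no analysis week for CMAI or mADCS-CGIC ratings taken at an ET visit, although the primary mixed model uses week as a factor.

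**Working it through.** **Inputs.** Visit 6 is Day 36 ± 3 and Visit 7 is Day 43 ± 3 (schedule). Per arm, 145 are randomized for 100 completers with about 30% dropout (Sample Size Determination). The gap g between last dose and ET visit is not given; 3, 7 and 14 days are assumptions.

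**1. The plan's own figure.** A completer takes the last dose in clinic at Visit 6: 36 + 7 = 43. This reproduces the printed Day 43, and for completers all three statements agree at the nominal days.

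**2. Early terminators.** Let the last dose be on day D and the ET visit on day D + g. Footnote a puts follow-up on day D + g + 7.

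| g (days) | Follow-up, days after last dose | Days beyond the 7-day limit |
|---|---|---|
| 0 | 7 | 0 |
| 3 | 10 | 3 |
| 7 | 14 | 7 |
| 14 | 21 | 14 |

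The dates coincide only at g = 0. The X in the last-dose row, read as printed, gives exactly that. No footnote confirms that it applies at ET, and the synopsis and schedule do not cover a subject who stopped drug earlier.

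**3. What the TEAE table needs.** It needs one end date per subject. The definition supplies one in its parenthesis, day D + 7, which does not depend on g. Since D + g + 7 is never earlier than D + 7, the nominal contact under footnote a always comes after that window has closed. Nothing inside the window is lost; a later non-serious event is simply past the cutoff. Dosing times are recorded in the Caregiver Diary, so D is available.

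**4. Completers as a benchmark.** If the ± 3-day tolerances on Visits 6 and 7 apply independently, a completer's gap from last dose to follow-up runs from (43 − 3) − (36 + 3) = 1 day to (43 + 3) − (36 − 3) = 13 days. The 10 days found at g = 3 lie inside that range; 14 and 21 days lie outside it. The visit date is therefore not a uniform endpoint for completers either, which is a reason to read the printed seven days as the operative limit.

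**5. How many subjects.** Expected dropouts per arm are 145 × 0.30 = 43.5, or 145 − 100 = 45. That is a ceiling, not the number affected. A subject's TEAE status changes only if g exceeds 0, the ET and follow-up contacts both take place, a non-serious event starts on days 8 to 7 + g after the last dose, and that subject is not already counted in the same table row. The documents give no rate for any of these.

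**6. ET ratings.** The visit tolerances cover Days 5–11, 12–18, 19–25 and 33–39. Of Days 2–32, 3 days (2–4) and 7 days (26–32) fall outside them: 10 of 31, or 32%. These are tolerances for scheduling visits, not analysis windows, so a day outside them shows no error in the schedule.

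**The case for a change.** The best argument for a change is that the literal reading of the last-dose row is not secure. Footnotes c and j show that entries in the shared column do not all apply alike to Visit 6 and ET. Adverse dropouts are a listed safety measure, and it is reasonable to expect that some of those subjects stop tablets before they attend. The phrase "through follow up (7 days after the last dose") names an event and a number together, and a programmer could choose the event. On that choice the window does lengthen for withdrawn subjects. With 15 mean treated days assumed for early terminators, arm person-days are 100 × 43 + 45 × 22 = 5,290. The extra 45g is 135, 315 or 630 days at g = 3, 7 or 14, which is 2.6%, 6.0% or 11.9%. A clarification would cost a few words.

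Part of this stands. A subject who stopped before the ET day is not expressly covered, and footnote a, the last-dose row and the synopsis sentence would read better if the sponsor reconciled them. Whether a withdrawing subject is dosed at ET is for the sponsor to say, and nothing here depends on the answer.

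The rest is weaker. The synopsis sentence describes the scheduled visit sequence and prints the completer's day; footnote a is the particular rule for those who withdraw. For g above 7, the last-dose anchor would put follow-up before the ET visit itself, which suggests that the synopsis sentence was not written for these subjects. The person-day percentages assume both g and the treated days, take every dropout to have the gap, and describe a quantity the plan does not report: it tabulates numbers and percentages of subjects with TEAEs.

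On ET ratings, a windowing rule is ordinary analysis detail, and any particular rule is debatable. Days 30–32 are 6 to 4 days from Day 36 but 8 to 10 from Day 22, so assigning them to Week 3 is not obvious. Preferring a scheduled score within a week would also discard late ET scores for subjects who attended Visit 5.

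**Conclusion.** No change to the plan follows. The three statements can diverge for a subject who stops drug before the ET day, by exactly the length of that gap, but this is an ambiguity rather than a contradiction. Read as printed they agree, and the TEAE definition already carries the numeric limit that an amendment would ask for. An analyst who applies that limit to every subject gets the same window after the last dose in each arm, whatever date the follow-up contact took place.

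The size cannot be computed, because the documents give neither the gap nor the event rate after the last dose. It is probably small, since several conditions must hold together before any subject's count changes. The primary efficacy analysis and sample size do not depend on the follow-up date, and the serious-event window is tied to the last dose alone. The unstated analysis week for ET ratings is a gap that analysts fill with a windowing rule.

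This conclusion rests on taking the seven days in the TEAE definition as the operative limit, and on the synopsis and schedule alone; fuller protocol or SAP text may settle both matters.
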